All subjects will receive premedication with H1- and H2-blockers (refer to Section [6.6.1](#)) and corticosteroids as prophylaxis (refer to Section [6.6.2](#)). Toxicity post-AL101 administration will be managed as specified in Section [6.4](#).

During the treatment period, subjects will undergo radiographic assessments every 8 weeks (± 3 days) for review by the investigator. Radiographic scans will also be collected and held for possible future retrospective independent evaluation. Other assessments will be done as specified in the Schedule of Activities ([Table 1](#)). A repeat of tumor imaging will be required for the purposes of confirmation of response (i.e., partial response, and/or complete response). The confirmation scan should be no earlier than 4 weeks following the first indication of response.

Samples from tumor biopsies will be collected at screening from a locally advanced or metastatic lesion (fresh or archival within 2 years), and at Cycle 4 Day 1 ±28 days (provided that biopsy collection is medically safe and not contraindicated). If an archival tumor block or 25 unstained slides are not available, the subject will be required to have a fresh tumor sample obtained at screening. Biopsy samples will be evaluated by NGS for genomics, immunohistochemistry (IHC) for Notch intracellular domain (NICD) stain, and other biomarkers potentially related to sensitivity to AL101 or TNBC prognosis. Blood samples for pharmacokinetics (PK) and biomarker analysis will also be collected on the same day as the on-treatment biopsy.

All subjects will undergo end of study (EOS) visit 30 days post last treatment with IP and will be contacted to determine survival status at timepoints specified in study duration. In subjects who discontinued IP due to toxicity, radiographic imaging will be done every 3 months until disease progression or until the subject initiates another anti-cancer therapy.

Disclosure Statement

This is a single group treatment study with no masking.

Number of Subjects

Using the Simon two-stage optimal design (targeting a response of 23% or greater), up to 67 to 73 subjects will be enrolled, depending on IP dose evaluated in Stage 1 and Stage 2 as follows:

- if the AL101 dose is 6 mg QW throughout the study, there will be up to 67 subjects evaluated, including the 6 subjects in the lead-in cohort for the Stage 1 evaluation.

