- c. Tumor biopsies (a resection, or core needle or punch biopsy with 20 gauge or larger and at least 2 passes) will be collected both at screening (fresh or archival within 2 years, from the same biopsy used for pre-screening), and at Cycle 4 Day 1 ± 28 days (fresh biopsy, provided medically safe and not contraindicated). If a tumor block or 25 unstained slides are not available, the subject will be required to have a fresh tumor sample obtained at screening from a readily accessible persistent locally advanced or metastatic lesion.
- d. Complete physical examination at baseline (refer to Section 8.2.3 for body systems to be evaluated) and every odd cycle thereafter or as clinically indicated; targeted physical examination at other time points.
- e. Refer to Section 10.2 for list of parameters
- f. Refer to Section 10.2 for list of parameters
- g. Screening laboratory may be used if conducted within 3-7 days of CID1.
- h. Chemistry will be conducted every week for the first 3 cycles and then every 4 weeks, with the exception of liver function tests (aspartate aminotransferase/alanine aminotransferase/alkaline phosphatase/bilirubin) which will be done weekly until week 32, and then every 2 weeks thereafter
- i. Coagulation factors will be done on Day 1 of every other cycle (e.g., C3D1, C5D1...)
- j. Urinalysis performed at Screening and as clinically indicated. Refer to Section 10.2 for list of parameters
- k. Pre-menopausal female subjects of childbearing potential only. Urine or serum pregnancy tests are acceptable.
- l. In the event of possible abnormal ECG findings, per the discretion of the investigator, additional ECG reads could be added at follow-up visits. The ECG evaluation will be performed locally; single ECG will be collected pre-dose (within 1 hour of infusion) and post-dose (within 1 hour post end of infusion). Clinically significant ECG abnormalities will be recorded on the electronic case report form (eCRF).
- m. CT or MRI with contrast are acceptable. Refer to Table 5 for imaging requirements during the study.
- n. For known or suspected brain metastases at baseline repeat brain MRI (preferred)/CT (acceptable) with contrast every 12 weeks. Conduct brain MRI/CT with contrast when subject has clinical symptoms. Same modality should be used throughout the study.

- o. During long-term follow up, subjects will be contacted every 3 months for the first years after EOS, then every 6 months for the next 2 years and then annually

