7.2. Discontinuation of Investigational Product

In some instances, it may be necessary for a subject to permanently discontinue IP.

Dosing of IP must be interrupted for any serious adverse reactions assessed by the investigator as related to IP. Restart of dosing may be considered upon approval by the Sponsor's Medical Monitor (or designee) after resolution of IP treatment-related events to baseline.

Discontinuation of IP does not represent withdrawal from the study. Subjects may withdraw or be withdrawn from IP at any time.

A subject may discontinue IP for reasons including but not limited to:

- Adverse event
- Death
- Lost to follow-up
- Non-compliance with study drug
- Physician decision
- Pregnancy
- Progressive disease
- Protocol deviation
- Study terminated by Sponsor
- Withdrawal by subject

The reason for subject discontinuation from IP will be recorded in the eCRF.

Please refer to [Section 6.4](#) for AL101 dose modifications and toxicity management which may lead to IP discontinuation. Pregnancy is a mandatory criterion for permanent discontinuation of IP. Any subject being managed with dose interruption for toxicity should have their study assessments followed per SoA.

All subjects who permanently discontinued IP will undergo an End of Study visit. For subjects who have discontinued IP due to reasons other than disease progression, tumor assessment will be continued at the protocol-specified schedule until documented disease progression or initiation of subsequent anticancer therapy, whichever comes first. See SoA ([Section 1.3](#)) for data to be collected at the End of Study visit.

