8. STUDY ASSESSMENTS AND PROCEDURES

- Study procedures and their timing are summarized in the SoA. Protocol waivers or exemptions are not allowed.
- Immediate safety concerns should be discussed with the Sponsor immediately upon occurrence or awareness to determine if the subject should continue or discontinue IP.
- Adherence to the study design requirements, including those specified in the SoA, is essential and required for study conduct.
- All screening evaluations must be completed and reviewed to confirm that potential subjects meet all eligibility criteria. The investigator will maintain a screening log to record details of all subjects screened and to confirm eligibility or record reasons for screening failure, as applicable.
- Procedures conducted as part of the subject's routine clinical management (e.g., blood count) and obtained before signing of the ICF may be utilized for screening or baseline purposes provided the procedures met the protocol-specified criteria and were performed within the time frame defined in the SoA.

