8.1.1. Response Evaluation Criteria in Solid Tumors (RECIST) v1.1

The primary efficacy endpoint, ORR, will be evaluated using RECIST v1.1 ([Eisenhauer, 2009](#)) as described in Section 10.6 (Appendix 6). A repeat of tumor imaging will be required for the purposes of confirmation of response (i.e., partial response, and/or complete response). The confirmation scan should be no earlier than 4 weeks following the first indication of response.

In addition to local imaging assessments performed by the investigator, scans will be collected and held for possible future retrospective independent evaluation. The investigator is responsible for diagnostic and treatment decisions concerning their subjects.

Disease staging will be collected at diagnosis and Screening for this protocol, prior to any treatment initiation. The minimum duration of stable disease will be defined as ≥ 4 weeks in determining the best overall response. To document evidence of prior disease progression, tumor measures prior to baseline assessments may be requested by the Sponsor.

The imaging requirements are provided in [Table 5](#).

Table 5 Imaging Guidelines

Study Period	Schedule	Imaging (RECIST 1.1)
Screening	Within 28 days prior to day 1	
At screening, the following imaging scans are required:
 
 1. Brain MRI (preferred) or CT (acceptable) with contrast 2. CT of chest 3. CT of abdomen 4. CT of pelvis 5. Bone scan
Treatment	Every 8 weeks (\pm 3 days) until disease progression	
Follow-up scans at 8-week intervals, the following image scans are required:
 
 1. Brain MRI/CT with contrast for known or suspected disease, can be done every 12 weeks; same modality as screening should be used throughout the study. 2. CT of chest 3. CT of abdomen 4. CT of pelvis 5. Bone scan to be done every 16 weeks, if bone metastases at Screening
End of Study(EOS) Visit	30 days post last IP (\pm 7 days)	
At EOS, the following image scans are required:
 
 1. Brain MRI/CT with contrast for known or suspected disease; same modality throughout the study. 2. CT of chest 3. CT of abdomen 4. CT of pelvis 5. Bone scan, if indicated for known or suspected disease

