Long-Term Follow-up	Every 3 months (\pm 7 days) until disease progression or until the subject initiates another anti-cancer therapy	
Only in subjects who discontinued IP due to toxicity, the following Long-Term Follow-up image scans are required:
 
 1. Brain MRI/CT with contrast for known or suspected disease; same modality throughout the study. 2. CT of chest 3. CT of abdomen 4. CT of pelvis 5. Bone scan, if indicated for known or suspected disease
Confirmation of Response Scan	The confirmation scan should be no earlier than 4 weeks following first indication of response (PR or CR)	
For confirmation no earlier than 4 weeks following a PR or CR, the following are required:
 
 1. Brain MRI/CT with contrast for known or suspected disease; same modality throughout the study. 2. CT of chest 3. CT of abdomen 4. CT of pelvis 5. Bone scan, if indicated for known or suspected disease

8.1.2. Patient Reported Outcome: European Organization for Research and Treatment of Cancer Quality of Life Questionnaire 30 questions (EORTC QLQ-C30) and Breast Cancer 45 Questions (EORTC QLQ-BR45)

The EORTC QLQ-C30 and EORTC breast cancer module QLQ-BR45 will be administered during the study every 4 weeks before IP administration.

EORTC QLQ-C30 was developed as an instrument to measure cancer subjects' physical, psychological and social functions (Kaasa, 1995). The questionnaire is composed of 5 multi-item scales (physical, role, social, emotional and cognitive functioning) and 9 single items (pain, fatigue, financial impact, appetite loss, nausea/vomiting, diarrhea, constipation, sleep disturbance and quality of life) (Kyriaki, 2001). It is validated and reliable and has been used successfully in various types of cancer, including BC (Mierzynska, 2020).

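### Section 7.2 and Table 5 conflict on who is scanned for progression after the EOS visit, and possibly on how often

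*Combined protocol and SAP*

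**What the plan says.** Section 7.2 sets the rule by exclusion. "For subjects who have discontinued IP due to reasons other than disease progression", it says, "tumor assessment will be continued at the protocol-specified schedule until documented disease progression or initiation of subsequent anticancer therapy". It does not say which schedule it means.

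Table 5 in Section 8.1.1 has a row for each study period:
- Treatment: scans every 8 weeks (±3 days) until disease progression.
- EOS: scans for all subjects, "30 days post last IP" (±7 days).
- Long-Term Follow-up: every 3 months (±7 days), but "Only in subjects who discontinued IP due to toxicity, the following Long-Term Follow-up image scans are required".
- Confirmation of response: no earlier than 4 weeks after a first PR or CR, with no restriction by reason for stopping.

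Sections 1.1 and 4.1 name the same narrow group, without the word 'only': "In subjects who discontinued IP due to toxicity, radiographic imaging will be done every 3 months". In the Schedule of Activities (Section 1.3), the long-term imaging cell carries footnote m: "Refer to Table 5 for imaging requirements during the study".

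**The concern.** Section 7.2 imposes a duty on a wide group, and the only post-EOS row in the imaging table serves part of that group. Sites work from the schedule, and Section 8 tells them to: "Adherence to the study design requirements, including those specified in the SoA, is essential and required for study conduct". Two other places point the same way. Section 4.5 treats a subject as having completed the study at the EOS visit, and Section 10.1.5 mentions only overall survival as collected beyond the 30-day visit.

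PFS and DOR run to the first documented progression or death (Section 9.3.3.1), and PFS at 6 months is a listed secondary endpoint. If scanning ends at EOS for some subjects who have not progressed, their later progression may never be documented. Section 9.3 plans Kaplan-Meier summaries, and Section 9.3.3.1 gives a censoring rule for OS only. Stops decided by the physician or the subject may be related to prognosis, so censoring at EOS could be informative. A later SAP can define censoring, but it cannot recover scans that were never taken.

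**Working it through.** **Who is scanned after EOS.** Section 7.2 lists ten reasons for stopping IP. Disease progression is outside its continuation rule. Toxicity stops have a Table 5 row. Continued scanning is not in question after death, loss to follow-up or study termination. I leave pregnancy aside. At least three reasons remain, plus part of a fourth:

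| Reason for stopping IP | Section 7.2 | Table 5 after EOS | Sections 1.1, 4.1 |
|---|---|---|---|
| Toxicity | continue | every 3 months | every 3 months |
| Non-compliance | continue | none | not named |
| Physician decision | continue | none | not named |
| Protocol deviation | continue | none | not named |
| Withdrawal from IP only | continue | none | not named |

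The Schedule of Activities does not break the tie, because footnote m leads back to Table 5.

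**How often.** The schedule that Section 7.2 leaves unnamed can be read in two ways:
- Long-Term Follow-up row: 3-monthly, but with no entry for the last four rows above.
- Treatment row: 8-weekly until progression. This covers everyone, but contradicts the 3-month interval for toxicity stops in Sections 1.1 and 4.1 and Table 5.

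Neither reading reconciles the text.

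**Timing against the 6-month landmark.** Days are counted from first dose. Six months = 365.25/2 = 182.6 days; 3 months = 365.25/4 = 91.3 days. The EOS scan falls at last dose + 30, at the latest + 37.

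Under Table 5, for a non-toxicity stop:
- The EOS scan cannot reach 6 months if the last dose is before day 182.6 − 37 = 145.6.
- With no dosing delays, C6D1 is day 5 × 28 = 140, and 140 + 37 = 177, which is before 182.6.
- C6D8 is day 147: 147 + 30 = 177 and 147 + 37 = 184, so it reaches 6 months only late in the window.

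Example, last dose at C3D22 = 2 × 28 + 21 = day 77:
- EOS scan: 77 + 30 = day 107 (100 to 114). It falls 182.6 − 107 = 75.6 days short of 6 months.
- 8-weekly from first dose: 2 × 56 = day 112 and 3 × 56 = day 168, both before 6 months.
- 3-monthly, counted from EOS (an assumption): 107 + 91.3 = about day 198, after 6 months.

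On the 3-monthly schedule, progression between day 107 and day 182.6 would first be documented near day 198, and the subject would count as progression-free at 6 months. The pattern starts at a last dose of about C3D8 (63 + 30 + 91.3 = 184.3) and holds through C6D1. At C3D1 the next scan would still fall in time (56 + 30 + 91.3 = 177.3).

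The documents give no rate of non-progression, non-toxicity stops, so the effect on any estimate cannot be calculated.

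**The case against.** The strongest reply is that Section 7.2 already orders the scans. The Treatment row ends at progression and not at the end of IP, so a careful site could continue 8-weekly imaging for everyone. This stands in part. It rules out the flat statement, which a reader might infer from Table 5 alone, that the protocol provides no scan after EOS for these subjects. It does not remove the conflict: that row is headed Treatment, and the Long-Term Follow-up row says 'Only'. It also defeats another tempting inference, that toxicity stops are untouched, because on this reading they have two intervals.

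A second reply is that the consequence is small or conjectural. The affected reasons are few, AL101 is infused on site, the endpoints are descriptive, and detailed methods are deferred to the SAP. All of this is fair. Nor does Kaplan-Meier need every subject scanned at 6 months, so the distance from the last scan to the landmark shows neither bias nor its size. What remains is that missing scans cannot be restored by analysis.

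A third reply is that 3-monthly imaging, the obvious way to align the text, is not neutral. That is right: it may mean fewer scans than Section 7.2 intends, and it documents progression late for the 6-month endpoint.

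**Conclusion.** The inconsistency is in the current text and should be corrected. The sections disagree on the population scanned after EOS. If Section 7.2 refers to the Treatment row, they also disagree on the interval for toxicity stops. A site following the Schedule of Activities and Table 5 would schedule no progression scan after EOS for the non-toxicity group, with possible informative censoring of PFS, PFS at 6 months and DOR.

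The size is unknown and no bias figure is supported. The day counts assume the stated windows; the cycle labels assume no dosing delay; the day-198 figure assumes that the 3 months run from EOS.

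A reader might infer that the primary analysis is at risk. The documents do not support that: all subjects are scanned at EOS, the confirmation scan is not limited to toxicity stops, and the Simon test of ORR is the only significance test planned. OS is followed by survival contact and is not directly affected.

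**What to change.** **Population.** In Table 5 and Sections 1.1 and 4.1, replace the toxicity condition with discontinuation of IP for any reason other than disease progression.

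**Interval.** State one interval in Section 7.2 and Table 5, and carry it into Sections 1.1 and 4.1. The choice is the sponsor's. Keeping the 8-week schedule from first dose at least through 6 months protects PFS at 6 months; 3-monthly scans from EOS do not, for the last-dose range shown above.

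**Cost.** Amendment wording, and a few more scans than Table 5 now lists for the non-toxicity group, which Section 7.2 already requires. An 8-week choice would also add scans for toxicity stops relative to the present 3-month interval.

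**Separate minor corrections**, not part of the main point and with no analysis effect claimed:
- Sections 6.4 (interruption over 28 days) and 6.4.3.1 (Hy's Law) discontinue the subject from the study, where Table 3 and Sections 6.4.3, 7.2 and 8.3.5.4 speak of IP. Use IP throughout.
- The one-level reduction sentence in Section 6.4 does not match Table 3, which at 6 mg gives 2 weeks on / 1 week off for the first Grade 3 diarrhea or other related Grade 3 nonhematologic event. Make it refer to the tables.
- Diarrhea unresolved at 14 days leads to discontinuation of IP in Table 3 and Section 6.4.2 item 2, but to temporary discontinuation in item 3. The sponsor should choose one rule.

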8.2. Safety Assessments

Planned time points for all safety assessments are provided in the SoA (Section 1.3).

8.2.1. Medical History and Prior Therapies

Any clinically significant diseases in the prior 3 years including any co-morbid conditions requiring active treatment as well as significant surgeries will be documented in the medical history section of the eCRF. This includes prior medical history and treatment regimen for TNBC.

Abnormal physical examination finding and/or the diagnosis of concomitant disease resulting from assessment at Screening must be also documented in the medical history section.

Information on all interventions (systemic therapy, surgery, radiation treatment) related to the subject's cancer will also be collected. Radiology and photography reports from imaging conducted as routine care will be collected if available from the last 3 years.

8.2.2. Eastern Cooperative Oncology Group (ECOG) Performance Status

The Eastern Cooperative Oncology Group (ECOG) Performance Status will be used to assess subjects' performance status (Table 6).

Table 6 ECOG Performance Status
ECOG PERFORMANCE STATUS

Grade	ECOG
0	Fully active, able to carry on all pre-disease performance without restriction
1	Restricted in physically strenuous activity but ambulatory and able to carry out work of a light or sedentary nature, e.g., light housework, office work
2	Ambulatory and capable of all self-care but unable to carry out any work activities. Up and about more than 50% of waking hours
3	Capable of only limited self-care, confined to bed or chair more than 50% of waking hours
4	Completely disabled. Cannot carry on any self-care. Totally confined to bed or chair
5	Dead

8.2.3. Physical Examination

The complete physical examination will include appearance, eyes, ears, nose, head, throat, neck, lungs, heart, abdomen, extremities, skin, and musculoskeletal system.

Treatment directed physical examination, will be conducted as outlined in the SoA (Section 1.3).

Significant findings made after the start of IP which meet the definition of an AE must be recorded on the AE eCRF.

Height will be recorded at Screening and weight measurements using a medical scale will be recorded as outlined in the SoA.

Investigators should pay special attention to clinical signs related to previous serious illnesses.

8.2.4. Vital Signs

Vital signs (to be taken before blood collection for laboratory tests) will be measured at all study visits and will include heart rate, respiratory rate, temperature, and blood pressure (systolic and diastolic). Blood pressure and heart rate will be done at rest as per standard practice at the investigational site. Significant findings noticed after the start of IP and findings that worsen significantly, which meet the definition of an AE must be recorded on the AE eCRF.

8.2.5. Electrocardiogram

Single 12-lead ECG will be obtained and evaluated locally as specified in the SoA (Section 1.3). Additional timepoints may be added, as clinically indicated.

Subjects should be in the supine position after the subject has rested for at least 5 minutes. In the event of possible ECG findings, additional ECG reads could be added at follow-up visits. Clinically significant ECG abnormalities will be recorded on the eCRF.

8.2.6. Clinical Safety Laboratory Assessments

- See Appendix 2 (Section 10.2) for the list of clinical laboratory tests to be performed and to the SoA (Section 1.3) for the timing and frequency.

- The investigator must review the laboratory report, document this review, and record any clinically relevant changes occurring during the study in the AE section of the eCRF. The laboratory reports must be filed with the source documents. Clinically significant abnormal laboratory findings are those which are not associated with the underlying disease, unless judged by the investigator to be more severe than expected for the subject's condition.
- All laboratory tests with values considered clinically significantly abnormal during participation in the study or within 30 days after the last dose of IP should be repeated until the values return to normal or baseline or are no longer considered clinically significant by the investigator or medical monitor.
- If such values do not return to normal/baseline within a period of time judged reasonable by the investigator, the etiology should be identified, and the Sponsor notified.
- All protocol-required laboratory assessments, as defined in Appendix 2 (Section 10.2), must be conducted in accordance with the laboratory manual and the SoA (Section 1.3).
- Laboratory values which are abnormal AND lead to either a change in dose of the IP, the requirement for an intervention, the requirement for additional medications, or are felt to otherwise be medically important should be recorded as adverse events in the eCRF.

